exhibited a pronounced decrease in their measured VO_2 , a pattern which was not present in treated animals which did not experience subsequent hemodynamic instability (**Figure 3**). Having seen this pattern consistently in approximately $n=40$ animal experiments (weight range 2.5-4 kg), we hypothesize that in critically ill patients, VO_2 may decrease below the critical DO_2 and exhibit measureable, even striking, decreases prior to hemodynamic decompensation takes place. If this hypothesis is true, quantification of VO_2 may represent a new 'vital sign' which represents end organ oxygen delivery in critically ill patients. Identification of patients with pathologically supply dependent VO_2 may permit definitive interventions to take place, e.g. initiation of extracorporeal life support, prior to a life-threatening PLOC.

Study Objectives

Specific Aim 1. To demonstrate that oxygen consumption (VO_2) and superior vena cava (SVC) saturations can be safely and precisely measured continuously in newborns undergoing surgery for hypoplastic left heart syndrome (HLHS) or d-transposition of the great arteries with an intact ventricular septum (d-TGA/IVS).

Hypothesis: Measurement of these oxygen-based parameters will not be associated with an increased incidence of equipment-related adverse events (e.g. line displacements, inadvertent extubations) and will lead to precise and reproducible measurements of these important parameters.

Specific Aim 2. To determine whether postoperative loss of circulation (PLOC, defined as cardiac arrest requiring CPR, ECMO cannulation, or causing death) in these patients are associated with a change in oxygen consumption or SVC saturation prior to the event.

Hypothesis: PLOC will be associated with significant decreases in both oxygen consumption and SVC saturations for at least 10 minutes prior to the onset of cardiac arrest.

Specific Aim 3. To determine whether the addition of the oxygen-based measurements to standardly measured parameters (i.e. vital signs, near-infrared spectroscopy

[figure not shown]

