Figure 3. In a proof of concept study, VO_2 monitoring of rabbits (weight ~3 kg) undergoing a 30 minute period of observation, followed by a 15 minute period of asphyxia, then a post-asphyxial recovery. Exemplary VO_2 tracings shown of animals treated (blue line) and untreated (red line) with an intravenous formulation of oxygen which prevented severe hypoxemic-ischemic injury. Animals which suffered severe injury exhibited a significant decrement in VO_2 early during the recovery period, a pattern which worsened prior to post-asphyxial loss of circulation. Animals who experienced treated asphyxial injury had an unchanged VO_2 curve. **A central hypothesis of this study is therefore whether VO_2 may represent a sensitive, real-time, prospective, and non-invasive marker of circulatory failure and inadequate DO_2 in newborns at risk for this life-threatening problem.**

measurements, intermittent measurements of lactate and superior vena cava saturations) add power in predicting which patients will experience PLOC.

Hypothesis: Continuous measurements of VO₂ and SVC saturations will add significantly to our ability to predict which patients will undergo PLOC.

Study Design

We will prospectively and continuously measure VO₂ and SVC saturations in newborns undergoing stage I palliation (S1P) or hybrid palliation (HP) for HLHS (n=20) or arterial switch operation (ASO) for d-TGA/IVS (n=20), beginning at the time of first preoperative intubation and ending at the time of the first postoperative extubation. Newborns will be followed for the occurrence of PLOC as the primary endpoint. A study schematic is attached as **Appendix 1**.

Study Population

Inclusion criteria.

1. Patient from birth to 6 months of age
2. HLHS AND no prior operations AND planned S1P or HP
OR
d-TGA/IVS AND planned ASO
3. Written parental informed consent

Exclusion criteria.

1. Weight < 2 kg
2. Disease specific
 - A. HLHS patients: Infants whose surgical plan includes a neonatal biventricular repair will be excluded.
 - B. d-TGA/IVS patients: Newborns with any additional cardiac defect other than an atrial septal defect will be excluded.
3. Patients on ECMO preoperatively
4. Clinically significant tracheo-esophageal fistula or known preoperative air leak

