Quality in the data collected by the oxygen consumption monitor will be ensured by a self-test at startup according to the manufacturer's instructions. Further, anesthesiologist and respiratory care staff will be instructed to monitor for the degree of air leak from the respiratory system by calculating the difference between inspiratory and expiratory measured tidal volumes. If the airleak exceeds this value, air may be added to the tracheal tube cuff. We have shown that when this difference is <15%, VO_2 data are accurately measured in newborns.²⁴ Further, an absence of end-tidal CO_2 data will be used as a signal of an endotracheal tube disconnection and possible suctioning event. VO_2 measurements are known to be unstable for several minutes following suctioning²⁸, so we will exclude VO_2 data for 10 minutes following any ETT disconnect from analyses.

Figure 6. The oxygen-based monitoring and data collection systems utilized for this study are attached to a rolling pole which can be placed anywhere around the patient and easily moved for convenience and safety.

Data within the SVC monitoring probe will be ensured by an in vitro calibration prior to probe insertion. When ever the treating team sends a venous blood gas from the central venous line, the co-oximetry value will be entered into the machine and used to recalibrate the probe in real-time.

Quality in the transfer of data from the medical record to the spreadsheet will be ensured by an independent review of the primary data by a second member of the study team. Furthermore, when possible, the fields for data entry will contain 'Data Validation' functions (i.e. value will turn red if outside expected limits, and hard stops will be inserted for physiologically impossible values). Additionally, drop down lists will be utilized when possible to minimize data entry errors.

Data Analysis Plan

Patients will be divided into patients who do and do not experience PLOC. All variables will be normalized to hours prior to bypass, bypass time and hours post-bypass time, such that all data for a specific post-bypass time will be aligned between patients. All weight-dependent variables will be normalized to preoperative body weight. Using GraphPad Prism, each variable will be entered into a different column for analysis.

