Simple analyses (e.g. mean, standard deviation, tests for normality) will be completed within GraphPad. With regards to the primary endpoint, VO₂ measurements will be analyzed for 120 minutes prior to a PLOC event in cases, and a randomly selected 120 minute period in controls. Values will be compared between cases and controls using generalized estimating equations (GEEs) to account for the correlation of multiple measurements within the same patient and to compare means between cases and controls. A post-hoc broken stick analysis will be used to determine the time prior to the event at which the VO₂ changed in each patient experiencing an event. Data for HLHS and dTGA patients will be pooled together.

More complex analyses will be completed by a collaborating company called Etiometry (including [name] and [name], co-investigators on this study), with whom the PI and others within the CICU have an established relationship. Deidentified information will be sent to the company, who will complete further analyses.

Power Calculations and Sample Size

The measured oxygen consumption in neonates following S1P has been described as 86 ± 16 mL/min/m^{2.22}. A sample size that includes 3 cardiac arrest events would allow us to detect a true decrease of 53 mL/min/m² in oxygen consumption with 90% power and a significance level of 0.05 (two tailed). Based on the significant change in VO₂ noted in the animal studies preceding cardiac arrest, we do not feel that this number is an unreasonable number. In order to collect 3 patients meeting the endpoint, we predict that we will require 20 patients undergoing S1P.

Risks and Discomforts

Because this is a prospective, observational study which we do not expect to change the standard of care, the risks associated with this study are really those of the standard

of care. The VO_2 measurements will be taken using an FDA-approved device which samples gas from the side of the tracheal tube of each patient. In reality, the adapter used by the study monitor is smaller and lighter than than used in our current capnographs, so the risk of accidental endotracheal tube removal should be the same or lower.

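### Aim 2 predicts a fall before the event, but the one stated test compares average VO2 levels between patients over 120 minutes and would usually miss a short fall

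*Combined protocol and SAP*

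**What the plan says.** Study Objectives, Specific Aim 2, asks whether PLOC is "associated with a change in oxygen consumption or SVC saturation prior to the event". Its hypothesis is "significant decreases in both oxygen consumption and SVC saturations for at least 10 minutes prior to the onset of cardiac arrest".

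For the primary endpoint, the Data Analysis Plan says that VO2 "measurements will be analyzed for 120 minutes prior to a PLOC event in cases, and a randomly selected 120 minute period in controls". GEE is then used "to account for the correlation of multiple measurements within the same patient and to compare means between cases and controls". No baseline, time term, slope or group-by-time interaction is given. No contrast of any kind is given for SVC saturation.

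Three further statements bear on the point:

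- "A post-hoc broken stick analysis will be used to determine the time prior to the event at which the" VO2 changed. This is done only in patients who had an event.
- "Data for HLHS and dTGA patients will be pooled together".
- Under Quality control methods, the plan drops VO2 "data for 10 minutes following any ETT disconnect from analyses".

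**The concern.** The hypothesis is about change within a patient before the event. The stated test is about level between patients. The two can disagree in both directions.

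- **A real fall can be missed.** A fall confined to the end of the window is averaged with up to 110 minutes of pre-fall data.
- **A difference can appear without any fall.** Cases whose VO2 is steadily lower, or a control group with a different mix of diagnoses, give a mean difference although nobody's VO2 changed before the event.

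The broken-stick analysis does look at change over time. However, it is labelled post hoc, covers VO2 only and is not a test. Breakpoints can also be fitted to control windows, so case lead times without that reference are hard to interpret.

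**Working it through.** **Inputs from the documents.** VO2 86 ± 16 mL/min/m², 3 events, a decrease of 53, 90% power and two-sided 0.05 (Power Calculations and Sample Size); a 120-minute window (Data Analysis Plan); 20 HLHS and 20 d-TGA/IVS patients (Study Design).

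**Assumptions.** SD 16 is taken as the between-patient SD of a 120-minute mean. The fall is a step. Three cases are set against 17 controls (HLHS only) or 37 (both diagnoses).

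**1. The plan's own figure.** Two groups of 3, with a t critical value on 4 df and a normal quantile for power:

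(2.776 + 1.282) × 16 × √(2/3) = 53.0

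So 53 reproduces as a difference between two groups of patients in one value each. Applied to the 120-minute mean, it assumes a fall that fills the window.

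**2. Dilution.** With a group term only and equal minutes per patient, the GEE estimate is the difference in patient means (confirmed in statsmodels). A fall of 53 over the last w minutes shifts it by 53 × w/120. Power is from the two-sample t test on one mean per patient.

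| Fall lasts | Shift | Power, 3 v 17 | Power, 3 v 37 |
|---|---|---|---|
| 10 min | 4.4 | 7% | 7% |
| 30 min | 13.3 | 24% | 27% |
| 60 min | 26.5 | 71% | 77% |
| 120 min | 53 | >99% | >99% |

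With SD 10 to 24 instead of 16, power for the 10-minute fall stays between 5% and 11%. A 10-minute fall from 86 to zero shifts the mean by only 86 × 10/120 = 7.2 (power 10-11%). The mean difference needed for 90% power is 34.4 (3 v 17) or 32.0 (3 v 37), so a 53 fall must last about 120 × 34.4/53 = 78 minutes or 120 × 32.0/53 = 72 minutes.

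**3. A difference without a fall.** Cases steadily 34.4 lower, with no change at all, are declared different with 90% (3 v 17) or 94% (3 v 37) power.

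Pooling has a similar effect. If d-TGA and HLHS levels differ by δ, then 3 HLHS cases against 17 HLHS and 20 d-TGA controls differ by δ × 20/37. For δ = 10, 20 or 30 (assumed; no d-TGA figure is given) this is 5.4, 10.8 or 16.2, and the t test rejects in 7%, 12% or 16% of trials.

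**4. GEE standard errors.** With the default robust standard error and a z test, the group-only GEE rejects in 18-21% of simulated trials with no fall and in 21-24% with the 10-minute fall. It barely separates the two.

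**5. A change contrast.** One value per patient: mean of the last 10 minutes minus mean of the 60 minutes before the window, compared by Welch's test. Assumed: AR(1) correlation 0.9 between minutes, noise SD 5-12 and a stable patient level (SD 16).

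| Case noise | Power, 53 fall of 10-120 min | Power, 26 fall | Type I error |
|---|---|---|---|
| Same as controls | 95-100% | 59-99% | 7-8% |
| Doubled | 55-99% | 23-69% | 7-8% |

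A pooled-variance t test has type I error of 5-6% with equal noise but 21-27% with doubled case noise.

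The baseline must lie before the window. Taken from the first 60 minutes inside it, pooled-t power is 21-83% for a 110-minute fall and 5-6% for a 120-minute fall.

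**The case against.** **Ten minutes is only the minimum.** The Figure 3 legend describes animals whose VO2 dropped early in recovery and then worsened. A 120-minute mean can see that pattern, and a baseline just before the window may already be low. For a linear 53 fall (SD of change 10-16, Welch test for the change), the comparison is:

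| Fall develops over | Power, 120-min mean | Power, change |
|---|---|---|
| 2 h | 71-77% | 82-98% |
| 4 h | 96-98% | 55-84% |
| 6 h | 99% | 34-61% |
| 8 h | 99% | 24-44% |

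This stands as a limit of the change contrast, and it is why the mean should be kept and the baseline chosen for stability. It does not turn a comparison of levels into a test of change.

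**The change-contrast power depends on assumed noise.** This also stands. With an SD of change of 16 or 22.6, Welch power for a 53 fall is 84-86% or 64-67%. That is still far above 7% for a 10-minute fall.

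**The plan does not rule out a time term.** True, but it states the purpose of the GEE, and that purpose is comparing means. Aligning data to bypass time defines no pre-event baseline, and the further analyses by a collaborating company are not described. With about 3 events, the choice of model should not wait for the data.

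**Conclusion.** The concern holds. The stated analysis does not test what Aim 2 hypothesises, and SVC saturation has no stated contrast.

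A 53 mL/min/m² step fall lasting 30 minutes or less would be detected at most about a quarter of the time. A fall of that size filling most of the window would be detected, so the fault is limited to shorter falls and to how a positive result is read. The plan's figure of 53 is not itself in error.

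The dilution follows from arithmetic alone. The power figures rest on SD 16, a step fall and 3 cases; those for the change contrast rest also on assumed noise. Three cases leave any result fragile. The plan should be changed before analysis.

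**What to change.** 1. Prespecify the test of Aim 2 as an own-baseline change or group-by-time contrast. One example is the mean of the last 10 analysable minutes minus the mean of a stable post-bypass period (such as 60 minutes) ending before the 120-minute window opens. State a fallback for patients with no such period.
2. Compare cases with controls by small-sample inference that allows unequal variance, such as Welch's test on one change per patient.
3. Keep the 120-minute mean as a supportive analysis; it covers slow falls.
4. Apply the same contrast to SVC saturation.
5. State the window rule when minutes are dropped after a tube disconnect, for example the last 10 analysable minutes within the final 30. Report how many patients needed it.
6. Run the same broken-stick fit on control windows as a reference for case lead times.

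**Cost.** Plan wording and some extra analysis, with no new patients or measurements. Study Design has measurement "beginning at the time of first preoperative intubation and ending at the time of the first postoperative extubation", so pre-window data should usually exist. The documents give no timing for PLOC, however, and an event soon after bypass may lack a stable baseline.

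In simulation, losing one of three cases to the disconnect exclusion cut Welch power for a 53 fall from 95-100% to 51-86%. The final-30-minute rule restored 95-100% for falls of 30 minutes or more. With one case's last 10 minutes excluded, it gave only 0-3% for a fall confined to those minutes. No window rule recovers a fall that lies wholly in excluded data.

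### The broken-stick fit that dates the VO2 change is run only in event patients, with no check that a break exists, so a lead time can be reported where VO2 did not change.

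*Combined protocol and SAP*

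**What the plan says.** Specific Aim 2 (Study Objectives) expects VO2 and SVC saturation to be reduced "for at least 10 minutes prior to the onset of cardiac arrest". For the primary endpoint, the Data Analysis Plan states: "VO₂ measurements will be analyzed for 120 minutes prior to a PLOC event in cases, and a randomly selected 120 minute period in controls". Means in cases and controls are compared by GEE. The timing step follows and is labelled post hoc: the broken-stick fit "will be used to determine the time prior to the event at which the VO₂ changed in each patient experiencing an event".

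The timing sentence names no window of its own. The plan does not say whether the first segment is flat or sloped, and requires no direction or minimum size of change. It gives no interval for the break time and no treatment of serial correlation. No fit in controls is mentioned.

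VO2 is recorded every second (Endpoints/Outcomes), over a period described in Study Design as "beginning at the time of first preoperative intubation and ending at the time of the first postoperative extubation". Data outside the 120 minutes will therefore usually exist.

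**The concern.** The GEE asks whether mean VO2 differs between cases and controls. It does not date a fall. The broken-stick fit is the only described analysis that estimates when VO2 changed, and so how much warning it might give.

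A least-squares broken stick picks the best-fitting break among the candidates and returns one even for a flat tracing. Physiological signals recorded each second are usually serially correlated, and slow wander looks like a segment with a slope. Without the same fit in patients who had no event, nobody can say how often a downward break 10 or more minutes before the end arises by itself.

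The Power Calculations section plans on 3 events. At the 10-15% event rate in the Background, 20 stage I patients give 20 × 0.10 = 2 to 20 × 0.15 = 3 expected events. One spurious lead time would be a third to a half of the timing evidence.

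**Working it through.** The plan states no figure for the accuracy of the break time, so there is none to reproduce. The check is by simulation.

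**Inputs from the documents.** Mean VO2 86 and planned decrease 53 mL/min/m² (Power Calculations and Sample Size); 120-minute window (Data Analysis Plan); 10-minute threshold (Specific Aim 2).

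**Assumed inputs.** One-minute values (120 per tracing); within-patient SD 8; AR(1) noise with lag-1 correlation from 0 to 0.95. The published SD of 16 describes a patient group and is not a within-patient figure.

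**Models.** Let t be minutes relative to the event and k the break.
- Two-slope: VO2 = a + b·t + c·max(t − k, 0), final slope b + c.
- Flat-then-slope: VO2 = a + c·max(t − k, 0), final slope c.

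The break k is the least-squares choice over a grid running from about 115 to 5 minutes before the end. The naive test is F = [(RSS0 − RSS1)/q] / [RSS1/(n − p)], ignoring autocorrelation. For the flat-then-slope form, q = 2 and n − p = 120 − 3 = 117.

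**Step 1: no true change (VO2 flat at 86).** Every tracing returns a break. Flat-then-slope form, 600 tracings per setting:

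| Lag-1 correlation | Median break, min before end | Downward and ≥10 min | Same, and naive F p<0.05 |
|---|---|---|---|
| 0 | 24 | 35% | 1% |
| 0.5 | 32 | 38% | 15% |
| 0.8 | 48 | 42% | 31% |
| 0.95 | 73 | 51% | 47% |

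The two-slope form, 1,000 tracings per setting, gives 39%, 44%, 49%, 50% and 50% for a downward break of at least 10 minutes at correlations 0, 0.5, 0.8, 0.9 and 0.95. Taking the runs together, about 40-50% is a fair summary. The joint figure with the naive test is about 3-47%, with a few points of variation by model form and run.

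**Step 2: size of the spurious falls.** At SD 8 the median fall is about 4-12 mL/min/m², rising with the correlation, and the largest seen was about 40. None reached 53. If 16 is used as a high value for the within-patient SD, about 2-3% reach 53 at the highest correlations.

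**Step 3: a true fall of the planned size inside the window.** With a fall of 53 starting 30 minutes before the event (SD 8, correlation 0.8 or 0.95), the fitted break has median 30 minutes and 10th-90th percentile about 23-42. The method works there.

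**Step 4: a fall running through the whole 120 minutes.** There is no bend to find.
- Two-slope form: median about 57-63 minutes, with the 10th percentile at about 6-22 and the 90th at about 101-113, depending on the correlation.
- Flat-then-slope form, true onset 180, 240 or 360 minutes: medians 107.5, 109.5 and 96 minutes. No estimate can pass the 115-minute search limit.

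**The case against.** The analysis is labelled post hoc and describes timing. The GEE, which does use controls and allows for within-patient correlation, tests whether VO2 differs. At the effect the study is designed for, the break is well located (step 3), and the spurious falls are small. All of this stands, and it limits the point to modest falls. It does not remove the point, because a difference in means does not show that any one patient's break time is real.

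Four stronger readings are tempting, and the documents do not support them.

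- *A lead time will be given for every event patient regardless.* The wording leans that way, but the plan is silent on a tracing without change and does not require a time.
- *The lead time is capped at 120 minutes and an earlier onset cannot be found.* The 120 minutes is stated only for the primary comparison. It is the natural reading for the fit as well, but longer recordings exist. The window also easily covers a 10-minute hypothesis; it would limit only an estimate of the full lead time.
- *The animal data show onset before the window.* The Figure 3 legend says that severely injured animals "exhibited a significant decrement in VO_2 early during the recovery period, a pattern which worsened prior to post-asphyxial loss of circulation". It gives no length for the recovery period and no time from decrement to loss of circulation.
- *With three cases and no signal, a false warning is nearly certain.* Compounding gives 1 − 0.60³ = 78% to 1 − 0.50³ = 88% for at least one downward break of 10 minutes or more. That counts falls of any size, so it is not the chance of a convincing false warning.

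**Conclusion.** The point holds for modest falls. As written, the timing analysis can return a lead time of 10 minutes or more from a tracing without change, and nothing in the plan shows how often that happens. The size is about 40-50% of flat tracings for any downward break, and about 3-47% if a naive F test is also required. The second range depends almost wholly on the autocorrelation, which is assumed.

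The claim does not extend to a fall of 53 mL/min/m²: at SD 8 no flat tracing produced one. The truncation problem in step 4 is conditional on the 120-minute window also governing this fit. This is worth correcting because the data for a better analysis are already being collected. It does not undermine the primary comparison.

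**What to change.** 1. Run the identical fit, with the analyst blinded to case status, in every control window. Use the same model form, break limits and handling of gaps from tube disconnections.
2. Report the direction, size and timing of control breaks beside the case results. With 40 patients and 3 events there would be 40 − 3 = 37 control tracings. At a 40% rate of downward breaks, the reference share has standard error √(0.40 × 0.60 / 37) = 0.08, which is precise enough to be useful.
3. Record a case as no change when its fall cannot be distinguished from those in control windows. Fix the rule before unblinding.
4. State the window. Where valid recording allows, fit a stretch longer than 120 minutes, with control windows of the same length. When VO2 is already falling at the start of the window, report onset earlier than X minutes instead of a time.

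The plan selects "a randomly selected 120 minute period in controls" and does not say that it is matched to cases on time since bypass. The control breaks are therefore an imperfect drift reference, and their post-bypass times should be reported.

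Cost: analysis wording and time only, with no new data. The downside is that reported lead times may look less favourable.

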In the BCH CICU, approximately 10-15% of neonates undergoing a stage I palliation (S1P) experience PLOC and receive some resuscitation, often times in the form of extracorporeal membrane oxygen (EMCO) device support. These patients often experience increased ICU and hospital lengths of stay, higher hospital morbidity and mortality, and worse neurologic outcomes.⁴⁻⁶ The purpose of this study is to determine whether continuous monitoring of VO_2 and SVC saturations will allow development of signs to predict which patients are at highest likelihood of experiencing a PLOC before the event, permitting time for interventions to take place prior to an injurious or potentially lethal event.

[figure not shown]

Figure 2. In patients born with an inadequate left ventricle, the right ventricle is used to pump blood to both the body and the lungs simultaneously and in parallel by connecting the pulmonary artery to the small aorta, and creating a shunt from this circulation to the lungs. This circulation leads to increased oxygen demand for the heart. When this demand is not met, myocardial dysfunction and PLOC result. Figure from Ohye, *NEJM*, 2010. {Ohye:2010kn}

Currently Used Markers of Oxygen Delivery

Assessing the physiologic state of patients is a complex but vitally important task. At the bedside, the clinician combines many pieces of data to assess the adequacy of end organ oxygen delivery, each of which has strengths and weakness as a clinical sign. Basic hemodynamic parameters (aka vital signs) include a patient's heart rate, arterial and venous blood pressures, oxygen saturations and temperature are central to the assessment of a patient's physiologic state, and are often the most important clues to inadequate oxygen delivery. Further to this includes markers of end organ function, such as urine output, coagulation parameter, as well as laboratory indices of hepatic and renal function add some degree of confidence that our general assessments are correct.

In patients at higher risk of insufficient DO_2 , advanced monitoring techniques are commonly used. The three most commonly used techniques in routine use in neonates undergoing congenital heart surgery include (1) cerebral near infrared spectroscopy (cNIRS), (2) SVC saturation sampling, and (3) serum lactate measurements.

Cerebral NIRS

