- Chest explorations and operative interventions performed at the bedside (e.g. clipping of BTS or Sano shunt) will be recorded each day from a review of the medical record, discussion with the primary team (including the bedside nurse) and the notes within the medical record.
 - Blood loss from chest tubes (in mL/kg each hour) and blood product administrations (including the blood products given and the times at which they are given) will be recorded from the medical record each day.
 - Sedatives and paralytics are routinely used and also affect oxygen consumption.
 - Diuretic medications are also routinely used, can affect preload.
 - Arrhythmias and
 - Other clinical parameters
 - Urine output is a crude marker of intravascular volume and end organ oxygen delivery.
 - The presence of enteral feedings, the rate of feedings and the caloric densities will also be recorded, as these may affect a patient's systemic vascular resistance.
 - Operative characteristics
 - Full preoperative and postoperative anatomic diagnoses
 - Residual anatomic defects
 - Total pump time, cross-clamp time, circulatory arrest time, regional perfusion time, minutes of continuous and modified ultrafiltration, blood products administered on bypass

Data Collection Methods, Assessments and Schedule

Outcome measurements

The majority of the endpoints presented above are routinely collected within the medical record as a part of patient care. Therefore, the majority of the data will be abstracted directly from the medical record and into a spreadsheet for data analysis by a member of the study team during each day for the duration of the study. The PI employs two full-time technicians within his lab who will assist with this labor intensive process.

- The oxygen-based measurements which are central to this study, including VO_2 , SVC saturation, as well as all ventilatory parameters listed above will be saved to a computer program (S5 Collect, GE Healthcare) attached to the patient's monitor. This program saves data in time stamped fashion Q1 second.
- Time-stamped vital sign data listed above will be exported daily from the hospital's in situ T3 program (Arcadia Solutions).
- The labs, treatments and other clinical parameters (see previous section) will be extracted in time-stamped fashion from the medical record each day by a member of the study team.

Patient variables

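### The primary VO₂ comparison pools HLHS and d-TGA with no diagnosis term; if all 3 expected events are HLHS, it carries 0.54 of any VO₂ difference between the diagnoses

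*Combined protocol and SAP*

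**What the plan says.** All references are to the combined protocol and SAP.

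- **Data Analysis Plan, groups.** "Patients will be divided into patients who do and do not experience PLOC".
- **Data Analysis Plan, windows.** "VO₂ measurements will be analyzed for 120 minutes prior to a PLOC event in cases, and a randomly selected 120 minute period in controls".
- **Data Analysis Plan, model.** GEE is used "to account for the correlation of multiple measurements within the same patient and to compare means between cases and controls". No covariate of any kind is listed.
- **Data Analysis Plan, diagnosis.** "Data for HLHS and dTGA patients will be pooled together".
- **Study Design.** 20 infants with HLHS (S1P or hybrid palliation) and 20 with d-TGA/IVS (arterial switch).
- **HLHS and the risk of PLOC.** "approximately 10-15% of neonates undergoing a stage I palliation (S1P) experience PLOC". No rate is given for the arterial switch.
- **Power Calculations and Sample Size.** To obtain 3 events, "we predict that we will require 20 patients undergoing S1P". The planning VO₂ is 86 ± 16 mL/min/m², for S1P only.

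The further analyses assigned to the collaborating company have no stated model.

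**The concern.** The projected events come from one diagnosis, while half of the enrolled infants have the other. Cases and controls would then differ in diagnosis as well as in outcome, and the pooled contrast mixes the two.

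If d-TGA infants have higher VO₂, part of a diagnosis difference is read as low VO₂ before PLOC, which is the study hypothesis. If they have lower VO₂, a real fall is understated. With about 3 cases, the data cannot separate these explanations unless diagnosis is in the model. The broken-stick analysis does not help: it is post hoc, covers event patients only, and makes no comparison with controls.

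**Working it through.** **The plan's own figure.** The plan states that 3 events detect a fall of 53 with 90% power (SD 16, two-sided 0.05). I could not reproduce this. A t test of 3 v 3 has 85.3% power at 53, and 90% power needs 57.4. For 3 v 37 the 90% detectable difference is 32.0. That is a separate matter; the share derived next does not depend on it.

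**Share of the diagnosis difference in the contrast.** Let D be mean VO₂ in d-TGA minus mean VO₂ in HLHS, and δ the true change before PLOC. Each patient has about equal weight. With 3 HLHS events:

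- case mean = μ + δ, where μ is the HLHS mean
- control mean = (17μ + 20(μ + D))/37 = μ + (20/37)D
- contrast = δ − (20/37)D = δ − 0.541D

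A rate of 10–15% in 20 infants gives 2 to 3 events, so other splits matter:

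- 2 HLHS events: 20/38 = 0.526
- 2 HLHS and 1 d-TGA event: 19/37 − 1/3 = 0.180

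**False-positive rate, no true change, d-TGA higher.** One mean per patient, SD 16, two-sided equal-variance t test, simulated. The values of D are assumptions.

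| D (mL/min/m²) | Bias, 3 HLHS | 3 HLHS | 2 HLHS | 2 HLHS + 1 d-TGA |
|---|---|---|---|---|
| 8 | 4.3 | 0.064 | 0.057 | 0.045 |
| 16 | 8.6 | 0.098 | 0.071 | 0.035 |
| 24 | 13.0 | 0.134 | 0.085 | 0.024 |
| 32 | 17.3 | 0.162 | 0.089 | 0.015 |

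With 3 HLHS events, D of 0, 2 and 4 gives 0.050, 0.051 and 0.053. With a diagnosis covariate the rate is 0.049–0.051 in every split. Most of the errors are false falls: at D = 8 they make up 5.7 of the 6.4 percentage points, against a nominal 2.5.

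**True fall of 53, d-TGA lower, 3 HLHS events.** Estimate = 53 − 0.541 × |D|.

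| d-TGA lower by | Estimated fall | Power |
|---|---|---|
| 8 | 48.7 | 99.8% |
| 16 | 44.4 | 98.9% |
| 24 | 40.0 | 94.7% |
| 32 | 35.7 | 80.5% |

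**Price of adjusting.** With 3 HLHS events the unadjusted SE is 16√(1/3 + 1/37) = 9.60. With the covariate it is 16√(1/3 + 1/17) = 10.02, a ratio of 1.04.

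| Events | SE: pooled / covariate / HLHS-only | 90% detectable: pooled / covariate / HLHS-only |
|---|---|---|
| 3 HLHS | 9.60 / 10.02 / 10.02 | 32.0 / 33.4 / 34.4 |
| 2 HLHS | 11.61 / 11.93 / 11.93 | 38.6 / 39.7 / 40.9 |
| 2 HLHS + 1 d-TGA | 9.60 / 9.65 / 11.93 | 32.0 / 32.1 / 40.9 |

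**Check with the planned GEE.** The plan does not state its standard error. Assuming equal cluster sizes, an uncorrected robust SE and a z test, with 3 HLHS events, rejection at D = 0/8/16/24/32 is 0.207/0.238/0.323/0.447/0.580 pooled, and 0.178–0.180 throughout with the covariate. The excess at D = 0 comes from having few case clusters. Only the rise with D is due to pooling.

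**The case against.** **The key quantity is missing.** No d-TGA VO₂ appears anywhere in the documents, so no part of the assumed 8–32 range has support in them, and below about 4 the effect is negligible. This stands, and the claim must remain conditional. Equality cannot be presumed either. The section on HLHS and PLOC risk says single-ventricle circulation raises myocardial VO₂ disproportionately, and the section on oxygen delivery says VO₂ falls when delivery is critically low. These could act in opposite directions.

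**The event split is a projection.** Three is the upper end of 2–3, the HLHS arm may include hybrid patients, and one d-TGA event cuts the share to 0.18 and makes the t test conservative. This also stands, but 3 HLHS events is the plan's own expectation. The 0.54 needs roughly equal weight per patient; dropping VO₂ data for 10 minutes after tube disconnections could shift it slightly.

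**The larger error is elsewhere.** Under the GEE assumptions above, the few-cluster excess at D = 0 (0.207 − 0.05 = 0.157) exceeds the rise from pooling at 1 SD (0.323 − 0.207 = 0.116). The covariate leaves rejection near 0.18 with three HLHS events and about 0.28 with two. This is correct. The covariate removes the bias from diagnosis but does not restore nominal error.

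**Power at 53 hardly suffers.** It stays at 94.7% up to 1.5 SD. That is true, but the estimate is still biased.

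**Pooling does not literally forbid a covariate.** It does not, but none is named. If the pooling sentence refers only to the broken-stick analysis it follows, the primary comparison still has no diagnosis term.

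**Conclusion.** The concern holds as a conditional statement. On the plan's own event projection, with about equal weight per patient, the primary contrast carries 0.54 of any VO₂ difference between HLHS and d-TGA. The share is 0.53 with two HLHS events and 0.18 if one of three events is d-TGA. Whether a difference exists, how large it is and in which direction are not known from the documents; with no difference there is no bias. At an assumed 0.5–1 SD the t-test inflation is modest (6–10%). It reaches 16% only at 2 SD. The change is worth making because an already recorded variable removes a rival explanation of the main result at little cost.

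**What to change.** Replace the pooling sentence in the Data Analysis Plan with:

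> The primary GEE comparison of VO₂ between cases and controls will include diagnosis (HLHS or d-TGA/IVS) as a covariate. The HLHS-only comparison will be reported as a sensitivity analysis.

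The covariate version should be primary because it keeps every case, whereas the HLHS-only version loses one for each d-TGA event. If all events are HLHS, the two give the same point estimate in the patient-level calculation, so the sensitivity analysis is informative mainly when an event occurs in d-TGA.

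The cost is two sentences and no new data: the operative characteristics in Endpoints/Outcomes already include "Full preoperative and postoperative anatomic diagnoses". By the patient-level approximation the SE widens by 4% with three HLHS events, 3% with two, and 0.5% if one of three is d-TGA. In all of these the covariate analysis's detectable difference stays below the planned 53. The small-sample behaviour of the GEE standard errors needs its own remedy.
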